### **6.7.2 Gastrointestinal Disorders**

Gastrointestinal perforation, GI fistula, and intra-abdominal and pelvic abscess: After starting treatment, subjects should be monitored for early signs of GI perforation such as abdominal pain, nausea, emesis, constipation, and fever especially if known risk factors for developing GI perforation or fistula (Turnage and Badgwell 2016) are present. Discontinue study treatment and initiate appropriate management in subjects who have been diagnosed with GI perforation or fistula.

Diarrhea: Subjects should be instructed to notify their physician immediately at the first signs of poorly formed or loose stool or an increased frequency of bowel movements. Guidelines for the evaluation and management of diarrhea are shown in Table 6-5. Administration of antidiarrheal/antimotility agents is recommended at the first sign of diarrhea as initial management. Some subjects may require concomitant treatment with more than one antidiarrheal agent. When therapy with antidiarrheal agents does not control the diarrhea to tolerable levels, study treatment should be temporarily interrupted or dose reduced. When the diarrhea is controlled, retreatment with study treatment may be acceptable per investigator decision. In addition, general supportive measures should be implemented such as continuous oral isotonic hydration, correction of fluid and electrolyte abnormalities, small frequent meals, and stopping lactose-containing products, high-fat meals, and alcohol.

Recurrent or prolonged diarrhea can be associated with anal or perianal skin erosions which increase the risk for anal abscesses, fistulas, or proctitis. Good personal hygiene should be emphasized. Regular examinations of the perianal region should be performed whenever diarrhea has occurred during treatment. Infections of the perianal region should be treated per local guidelines.

**Table 6-5: Management of Diarrhea Associated with Cabozantinib**

| Status  | Management   |
|---|--|
| Tolerable Grade 1-2 (duration < 48 h)             | 
 
• Continue with study treatment and consider dose reduction
 
• Initiate treatment with an antidiarrheal agent (eg, loperamide 4 mg followed by 2 mg after each episode of diarrhea [maximum: 16 mg loperamide per day])
 
• Dietary modifications (eg, small lactose-free meals, bananas and rice)
 
• Intake of isotonic fluids (1-1.5 L/day)
 
• Re-assess after 24 hours:               
 
○ Diarrhea resolving to baseline bowel habits: gradually add solid foods and discontinue or decrease antidiarrheal treatment after 12 h diarrhea-free interval
 
○ Diarrhea not resolving: Continue/resume antidiarrheal treatment
 
 
 
   |
| Intolerable Grade 2, Grade 2 > 48 h, or ≥ Grade 3 | 
 
• Interrupt study treatment
 
• Ask subject to attend clinic
 
• Rule out infection (eg, stool sample for culture)               
 
○ Administer antibiotics as needed (eg, if fever or Grade 3-4 neutropenia persists > 24 h)
 
 
 
• Administer fluids (1-1.5 L/day orally or intravenously, as appropriate) for hydration or to correct electrolyte abnormalities
 
• For Grade 3-4 or complicated lower grade diarrhea consider hospitalization and IV hydration
 
• Re-assess after 24 h               
 
○ Diarrhea resolving to baseline bowel habits or Grade ≤ 1: consider restarting study treatment at reduced dose
 
○ Diarrhea not resolving: Start and/or continue antidiarrheal treatment (eg, loperamide 4 mg followed by 2 mg after each episode of diarrhea [maximum: 16 mg loperamide per day]). Consider starting second line antidiarrheal or referral to gastroenterologist
 
 
 
 |

Nausea and vomiting: Antiemetic agents are recommended as clinically appropriate for treatment or prophylaxis of nausea and vomiting, along with supportive care. Dehydration and electrolyte abnormalities may be associated with vomiting, and monitoring for and correction of fluid and electrolyte disturbances should be implemented. Antiemetic medications should be assessed for potential drug interaction (refer to Section 7.1.2.1 for further details).

### 6.7.3 Non-Gastrointestinal Fistula

Complications from radiation therapy especially of the thoracic cavity including mediastinum have been identified as a possible predisposing risk factor for non-GI fistula formation in subjects undergoing treatment with VEGF pathway inhibitors.

Discontinue study treatment and initiate appropriate management in subjects who have been diagnosed with a non-GI fistula.

#### **6.7.4 Hemorrhage**

Hemorrhagic events, including serious and sometimes fatal events, have been reported with cabozantinib. Subjects should be monitored for bleeding events with serial complete blood counts and physical examination while on study. The risk of hemorrhage in cabozantinib-treated subjects with brain metastases has not been thoroughly analyzed. Subjects enrolled with treated and stable brain metastases should be monitored with a high index of suspicion if symptoms that could be due to a CNS hemorrhage occur.

Study treatment should be discontinued in subjects with serious and life-threatening bleeding events or recent hemoptysis ( $\geq 2.5$  mL of red blood).

#### **6.7.5 Thromboembolic Events**

Thromboembolic events are frequent in cancer subjects due to procoagulant changes induced by the malignancy or anticancer therapy. DVT and pulmonary embolism have been observed in clinical studies with cabozantinib, including fatal events. Subjects who develop a pulmonary embolism and/or DVT should have study treatment interrupted until therapeutic anticoagulation is established. Treatment may be resumed in subjects with pulmonary embolism or DVT if it is determined that the event is uncomplicated, the subject is deriving clinical benefit from study treatment, and anticoagulation does not place them at a significant risk that outweighs the benefit of resuming treatment per discretion of the investigator and according to individual protocols. Low molecular weight heparins are the preferred management for thrombotic events; oral anticoagulants (eg, warfarin or other coumarin-related agents, direct thrombin or direct FXa inhibitors, or antiplatelet agents) are not allowed.

Arterial thrombotic events (eg, TIA, MI) have been observed in studies with cabozantinib. Further treatment should be discontinued in subjects who develop an acute MI, cerebral infarction, or any other clinically significant arterial thromboembolic complication.

#### **6.7.6 Hypertension**

Table 6-6 provides treatment guidelines for hypertension deemed related to cabozantinib. Blood pressure should be monitored in a constant position visit to visit, either sitting or supine in a relaxed setting. Decisions to reduce or interrupt the dose of study treatment must be based on BP readings taken by a medical professional and must be confirmed with a second measurement at least 5 minutes following the first measurement.

Study treatment should be discontinued in subjects with hypertensive emergency.

**Table 6-6: Management of Hypertension Associated with Cabozantinib**

| Criteria for Dose Modifications  | Treatment Dose Modification   |
|--|---|
| Subjects NOT receiving optimized anti-hypertensive therapy                                    |   |
| > 150 mm Hg (systolic) a and < 160 mm Hg
OR
> 100 mm Hg (diastolic) and < 110 mm Hg | 
 
Optimize antihypertensive medications by adding new or additional antihypertensive medications and/or increase dose of existing medications.
 
Reduce study treatment by one dose level if optimal antihypertensive therapy (usually to include 3 agents) does not result in BP < 150 mm Hg systolic or < 100 mm Hg diastolic
 
If subject is symptomatic interrupt study treatment
 
   |
| ≥ 160 mm Hg (systolic)
OR
≥ 110 mm Hg (diastolic)  | 
 
Reduce study treatment by one dose levelb or interrupt study treatment per investigator discretion
 
Add new or additional anti-hypertensive medications and/or increase dose of existing medications and monitor subject closely for hypotension. If optimized antihypertensive therapy (usually to include 3 agents) does not result in BP < 150 mm Hg systolic or < 100 mm Hg diastolic, study treatment should be dose reduced further or interrupted
 
Study treatment should be dose interrupted if upper limits of systolic BP (≥ 160 mm Hg) are sustained and not adequately manageable or if systolic BP is > 180 mm Hg or diastolic BP > 110 mm Hg, or if subject is symptomatic
 
Re-start study treatment at the most tolerable dose and re-escalate only if BP falls to and is sustained at < 150 mm Hg systolic and < 100 mm Hg diastolic
 
 |
| Hypertensive emergency c  | 
 
Discontinue study treatment
 
   |

BP, blood pressure.

a The investigator may decide to initiate or adjust antihypertensive treatment at a lower threshold than systolic BP >150 or diastolic BP >100 based on their clinical judgment and assessment of the individual subject.

b Permitted dose levels are defined by individual protocols.

c Hypertensive emergency is defined as uncontrolled elevated BP with clinical evidence of progressive or impending end-organ damage (eg, myocardial infarction/ischemia, intracranial hemorrhage, cerebral ischemia, pulmonary edema, encephalopathy, kidney damage).

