    - ii. Uncontrolled hypertension defined as sustained BP > 150 mm Hg systolic or > 100 mm Hg diastolic despite optimal antihypertensive treatment
    - iii. Stroke (including transient ischemic attack [TIA]), myocardial infarction, or other ischemic event, or thromboembolic event (eg, deep venous thrombosis [DVT], pulmonary embolism) within 6 months before randomization. Subjects with a more recent diagnosis of DVT are allowed if stable, asymptomatic, and treated with LMWH for at least 6 weeks before randomization.
  - b. Gastrointestinal disorders (eg, malabsorption syndrome or gastric outlet obstruction) including those associated with a high risk of perforation or fistula formation:
    - i. Tumors invading the GI tract, active peptic ulcer disease, inflammatory bowel disease, ulcerative colitis, diverticulitis, cholecystitis, symptomatic cholangitis or appendicitis, acute pancreatitis or acute obstruction of the pancreatic or biliary duct, or gastric outlet obstruction
    - ii. Abdominal fistula, GI perforation, bowel obstruction, or intra-abdominal abscess within 6 months before randomization  

Note: Complete healing of an intra-abdominal abscess must be confirmed prior to randomization
  - c. Clinically significant hematemesis or hemoptysis of > 0.5 teaspoon (> 2.5 mL) of red blood or history of other significant bleeding within 3 months before randomization
  - d. Cavitating pulmonary lesion(s) or known endobronchial disease manifestation
  - e. Lesions invading major pulmonary blood vessels
  - f. Other clinically significant disorders such as:
    - Active infection requiring systemic treatment, infection with human immunodeficiency virus or acquired immunodeficiency syndrome-related illness, or chronic hepatitis B or C infection
    - Serious non-healing wound/ulcer/bone fracture
    - Malabsorption syndrome
    - Moderate to severe hepatic impairment (Child-Pugh B or C)
    - Requirement for hemodialysis or peritoneal dialysis
    - Uncontrolled diabetes mellitus
    - History of solid organ transplantation

8. Major surgery (eg, GI surgery, removal or biopsy of brain metastasis) within 8 weeks before randomization. Complete wound healing from major surgery must have occurred 4 weeks before randomization and from minor surgery (eg, simple excision, tooth extraction) at least 10 days before randomization. Subjects with clinically relevant ongoing complications from prior surgery are not eligible.

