    - ii. Uncontrolled hypertension defined as sustained blood pressure (BP) > 150 mm Hg systolic or > 100 mm Hg diastolic despite optimal antihypertensive treatment
    - iii. Stroke (including transient ischemic attack [TIA]), myocardial infarction (MI), or other ischemic event, or thromboembolic event (eg, deep venous thrombosis [DVT], pulmonary embolism) within 6 months before randomization. Subjects with a more recent diagnosis of DVT are allowed if stable, asymptomatic, and treated with LMWH for at least 6 weeks before randomization.
  - b. Gastrointestinal disorders (GI; eg, malabsorption syndrome or gastric outlet obstruction) including those associated with a high risk of perforation or fistula formation:
    - i. Tumors invading the GI tract, active peptic ulcer disease, inflammatory bowel disease, ulcerative colitis, diverticulitis, cholecystitis, symptomatic cholangitis or appendicitis, acute pancreatitis or acute obstruction of the pancreatic or biliary duct, or gastric outlet obstruction
    - ii. Abdominal fistula, GI perforation, bowel obstruction, or intra-abdominal abscess within 6 months before randomization  
 Note: Complete healing of an intra-abdominal abscess must be confirmed prior to randomization
  - c. Clinically significant hematemesis or hemoptysis of > 0.5 teaspoon (> 2.5 mL) of red blood or history of other significant bleeding within 3 months before randomization
  - d. Cavitating pulmonary lesion(s) or known endobronchial disease manifestation
  - e. Lesions invading major pulmonary blood vessels

- f. Other clinically significant disorders such as:
- Active infection requiring systemic treatment, infection with human immunodeficiency virus or acquired immunodeficiency syndrome-related illness, or chronic hepatitis B or C infection
  - Serious non-healing wound/ulcer/bone fracture
  - Malabsorption syndrome
  - Moderate to severe hepatic impairment (Child-Pugh B or C)
  - Requirement for hemodialysis or peritoneal dialysis
  - Uncontrolled diabetes mellitus
  - History of solid organ transplantation
8. Major surgery (eg, GI surgery, removal or biopsy of brain metastasis) within 8 weeks before randomization. Complete wound healing from major surgery must have occurred 4 weeks before randomization and from minor surgery (eg, simple excision, tooth extraction) at least 10 days before randomization. Subjects with clinically relevant ongoing complications from prior surgery are not eligible.

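### Table 6-6 joins its post-optimization blood pressure target with *or*, so read literally a single raised limb on optimized therapy does not trigger the table's dose-reduction step

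*Combined protocol and SAP*

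**What the plan says.** Table 6-6 has two blood pressure rows, both under the heading "Subjects NOT receiving optimized anti-hypertensive therapy", and a third row for hypertensive emergency.

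- **Row 1** takes a subject whose systolic pressure is above 150 and below 160 mm Hg, OR whose diastolic pressure is above 100 and below 110 mm Hg. Antihypertensives are optimized first. Then: "Reduce study treatment by one dose level if optimal antihypertensive therapy (usually to include 3 agents) does not result in BP" below 150 systolic *or* below 100 diastolic. Symptomatic subjects are interrupted.
- **Row 2** takes a subject at systolic 160 or more, OR diastolic 110 or more. Bullet 1 requires a reduction of one dose level "or interrupt study treatment per investigator discretion". Bullet 2 adds antihypertensives; if the same *or* target is not reached, "study treatment should be dose reduced further or interrupted". Bullet 3 begins "Study treatment should be dose interrupted if upper limits of systolic BP" and covers a sustained systolic of 160 or more that is not adequately manageable, systolic above 180, diastolic above 110, or symptoms. Bullet 4 governs restart: "re-escalate only if BP falls to and is sustained at" below 150 systolic *and* below 100 diastolic.

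Elsewhere, exclusion criterion 7.a.ii in Section 4.3 reads "Uncontrolled hypertension defined as sustained blood pressure (BP) > 150 mm Hg systolic or > 100 mm Hg diastolic despite optimal antihypertensive treatment". The Synopsis and the crossover criteria in Appendix B define it in the same way.

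**The concern.** A subject enters either row because one limb is too high. The later test of whether treatment has worked is then written so that one limb being acceptable is enough. For a subject with only one limb raised, the acceptable limb can be the one that was never the problem.

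This is an operative dosing rule with numeric limits for a known cabozantinib toxicity. In the 25-subject Phase 2 study in Table 1-2, hypertension was reported in 6 + 5 + 1 = 12 subjects across Grades 1 to 3. Section 6.7.6 says decisions to reduce or interrupt must rest on confirmed readings by a medical professional, so sites are meant to work from the numbers. About 150 sites will apply the table, and the wording lets them apply it differently. What is at stake is subject safety and consistent dosing.

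**Working it through.** No figure in the plan needs reproducing; this is a check of logic. Write S for systolic and D for diastolic pressure (mm Hg) on optimized therapy.

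**Rule as written (row 1 bullet 2, row 2 bullet 2).** Act if NOT (S < 150 or D < 100). This is the same as: act if S ≥ 150 **and** D ≥ 100.

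**Rule with *and* in the target.** Act if NOT (S < 150 and D < 100). This is the same as: act if S ≥ 150 **or** D ≥ 100. It is the exact complement of the table's restart condition (S < 150 and D < 100).

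**Cases.** The third column applies the definition in criterion 7.a.ii and assumes the reading is sustained.

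| Reading | Meets row 1 entry | Uncontrolled by 7.a.ii | Acts as written | Acts with *and* | Re-escalation allowed |
|---|---|---|---|---|---|
| 158/88 | yes | yes | no | yes | no |
| 145/105 | yes | yes | no | yes | no |
| 155/105 | yes | yes | yes | yes | no |
| 145/95 | no | no | no | no | yes |

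The first two lines show the contradiction. The same reading counts as uncontrolled for eligibility and as too high for re-escalation, yet counts as on target for the reduction step.

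**Row 1 band.** I took integer readings with S from 120 to 159 and D from 70 to 109; the lower limits of the grid are an assumption.

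- Row 1 entry: systolic limb 9 × 40 = 360, diastolic limb 40 × 9 = 360, overlap 9 × 9 = 81, so 360 + 360 − 81 = 639 pairs.
- As written, the bullet acts on 10 × 10 − 1 = 99 of them (150/100 is excluded because it does not enter row 1).
- The other 639 − 99 = 540 have one limb at or above its limit and the other below. As written 0 of 540 act; with *and*, 540 of 540 act.

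All 540 already meet the literal target at entry, before any antihypertensive is added. These counts check the logic; they are not patient proportions.

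**Range affected.**

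- Row 1: S 150-159 with D < 100, or D 100-109 with S < 150. No reduction is triggered.
- Row 2: the same range, but only the *further* reduction or interruption is lost, because bullet 1 has already required a reduction or interruption. Readings of S ≥ 160 or D ≥ 110 meet row 2's own entry criterion, so bullet 1 applies to them, and the higher values also fall under bullet 3.

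The corrected rule and the eligibility definition differ only at exactly 150 or exactly 100, because the table's target uses *below* and the definition uses *above*.

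**The case against.** The strongest reply is that the protocol does not leave these subjects without guidance.

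- Section 6.7.1 names hypertension among early-onset events. It asks that reductions and interruptions be considered, and recommends reduction for events that could become serious or intolerable if they persist. Only afterwards does it list persistent uncontrolled hypertension as a reason to discontinue.
- Section 6.5.1 says reductions or interruptions should be considered when supportive care is ineffective, and separately allows them for toxicity of lower grade.
- Table 6-3 calls for interruption or reduction for Grade 3 events and for Grade 2 events that are intolerable and cannot be adequately managed.
- The literal reading is also one that few clinicians would adopt, since a subject entering for systolic pressure alone would be on target at once. Section 6.7.6 calls the table treatment guidelines, and read literally the bullets are silent; they do not direct a harmful act.

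Most of this stands. A reader might infer that a row 1 subject goes straight from optimized antihypertensives to discontinuation, or that no text supports reducing the dose. Sections 6.5.1 and 6.7.1 rule out both readings.

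The reply does not remove the error. The two sections give no blood pressure threshold and are worded more softly than the table's instruction to reduce. Table 6-3 gives no pressure limit either, and its note refers specific conditions to Section 6.7, which contains Table 6-6. That the intended meaning can be recovered shows this is a wording error; it does not make the sentence right.

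**Conclusion.** The point holds as a wording error in a safety dosing rule, and it should be corrected. As written, an asymptomatic subject on optimized therapy with one limb raised, in the range given above, does not trigger the table's reduction (row 1) or further reduction or interruption (row 2). What is lost is the table's explicit instruction with a pressure threshold; general guidance to reduce the dose remains.

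The finding rests on three conditions: a literal reading of *or*, an asymptomatic subject, and readings below the limits where row 2's bullets 1 and 3 apply. Table 6-3 may still reach some of these subjects by adverse event grade. The documents do not give the share of subjects with a single raised limb, so no count can be stated.

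A reader might also extend the row 2 range to a diastolic of 110, or look for an effect on the trial's inference. Neither is supported. A diastolic of 110 meets row 2's entry criterion, and the rule does not touch the endpoints, alpha or power.

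**What to change.** In the row 1 reduction bullet and the row 2 further-reduction bullet, change *or* to *and* in the target. Equivalently, state the trigger directly: act if, on optimized therapy, systolic pressure remains at or above 150 mm Hg or diastolic pressure remains at or above 100 mm Hg. Either form matches the restart bullet already in the table.

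The cost is one word in each of two bullets, handled as a protocol modification under Section 13, with a notice to sites. No new assessments or data are needed, and the SAP does not change.

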### 6.7.7 Stomatitis and Mucositis

Preventive measures may include a comprehensive oral examination to identify and treat any potential risk for complications before study treatment is initiated. Appropriate correction of local factors should be instituted as indicated, such as modification of ill-fitting dentures and appropriate care of gingivitis. During treatment, good oral hygiene and standard local treatments such as non-traumatic and non-irritating cleansing, and oral rinses (eg, with a weak solution of salt and baking soda) should be maintained. Lips should be kept moisturized with lip balm. The use of lipstick, lip-gloss, and Vaseline should be avoided.

Local treatment should be instituted at the earliest onset of symptoms. Obtain bacterial/viral culture if oral infection is suspected and treat infection as clinically indicated.

### **6.7.8 Skin Disorders**

Wound healing and surgery: Cabozantinib has the potential to cause wound healing complications and wound dehiscence which may even occur long after a wound has been considered healed. Therefore, surgical and traumatic wounds must not only be completely healed prior to starting study treatment but must also be monitored for wound dehiscence, wound infection and other signs of impaired wound healing while the subject is being treated with study treatment. If dehiscence occurs, study treatment should not be restarted until complete healing has taken place.

Study treatment should be stopped at least 28 days prior to scheduled surgery. The decision to resume study treatment after surgery should be based on clinical judgment of adequate wound healing.

Palmar-plantar erythrodysesthesia (also known as hand-foot syndrome), skin rash (including blister, erythematous rash, macular rash, skin exfoliation, dermatitis acneiform, and papular rash), pruritus, dry skin, erythema, pigmentary changes, and alopecia have been reported with cabozantinib. All subjects on study should be advised on prophylactic measures including the use of emollients, removal of calluses, avoidance of exposure of hands and feet to hot water leading to vasodilatation, protection of pressure-sensitive areas of hands and feet, and use of cotton gloves and socks to prevent injury and keep the palms and soles dry.

Early manifestations include tingling, numbness, mild hyperkeratosis, and symmetrical red and swollen areas on the palms and soles. The lateral sides of the fingers or periungual zones may also be affected. Adequate interventions are required to prevent worsening of skin symptoms such as blisters, desquamations, ulcerations, or necrosis of affected areas. Analgesics may be required for pain control.

Aggressive management of symptoms is recommended, including early dermatology referral. Treatment recommendations in response to PPE are summarized in Table 6-7.

